### 8. Post-Infusion Treatment:

Pharmacologic treatment will proceed as follows at the conclusion of post-infusion PET and MRI acquisition:

Study participants will receive six months of open clinical treatment in the form of:

- a) Continuation of inpatient treatment for as long as is clinically indicated, followed by
- b) Outpatient psychiatrist visits for medication management with a psychiatrist in MIND to complete a total of 6 months of psychiatric care inclusive of the inpatient stay.
  - 9. Exploratory research assessments of mood, suicidality, and side effects (per Fig. 1) Research assessments will continue for a three-week continuation phase post-infusion. Continuation phase clinical appointments will be weekly for four weeks, then decreasing to at least monthly, as clinically indicated, for the remainder of the six months.

Research assessments may be performed using phone or secure video (Webex or Zoom) and using Internet-based encrypted systems including Redcap or Citrix, managed by The NYSPI/Columbia School of Public Health Data Coordination Center (DCC).

You can upload charts or diagrams if any

# **Criteria for Early Discontinuation**

Criteria for Early Discontinuation

Withdrawal from Study: A subject will be withdrawn from the study if:

- a. Subject requests to be removed for any reason.
- b. The PI judges that it is medically unwise for the subject to continue in the study. For example, if the subject is unable to comply with the study procedures.

- c. The subject is unable to tolerate the delay to treatment because of pronounced worsening of symptoms such as marked agitation or psychotic symptoms. Worsening of suicidal ideation will not automatically require discontinuation from research, as long as the team judges that the subject can be managed safely as an outpatient (e.g. they have no plan or intent), or they agree to inpatient treatment and the inpatient staff agrees that the patient may continue research participation. A CGI≥5 will trigger conversation with study PI regarding possible study discontinuation.
- d. A rise in systolic blood pressure  $\geq$  200 mm Hg or diastolic blood pressure to  $\geq$  115 mm Hg during the infusion.
- e. During infusion, if O2 saturation remains <94% with nasal canula oxygen, then subject will be withdrawn from research and treated clinically.
- f. Other criteria for discontinuation will be appearance of psychosis, mania, severe agitation, or other deterioration where the treating physician decides that research participation is unacceptable.

# **Blood and other Biological Samples**

Please create or insert a table describing the proposed collection of blood or other biological specimens

Sample	Collection Time Point	Total Collected per Participant
Blood	Baseline (through protocol 4815): 43ml	Maximum blood drawn through both protocols collectively: ≤243ml
	Arterial blood sampling during PET scans, pre- and post-ketamine infusion: ≤100ml x 2 = ≤200 ml	

### **Assessment Instruments**

Create a table or give a brief description of the instruments that will be used for assessment

Domain Instrument	Time
-------------------	------

		100.45
Informed consent	IRB-approved form	30-45 min
Diagnosis	SCID-5	120 min
Demographics	Division Baseline	30 min
	Demographic form (BDEMO)	
Clinical State	Hamilton Depression Rating	10 min
	Scale 24-Item (HDRS- 24)	
	Beck Depression Inventory	10 min
	(BDI)	
	Profile of Mood States	10 min
	(POMS)	
	Clinical Global Impressions	1 min
	(CGI)	
	Brief Psychiatric Rating	5 min
	Scale (BPRS) – 4 item	
	positive symptom subscale	
Medication	Past and Current	10 min
	Medications List	
_	Systematic Assessment for	10 min
	Treatment Emergent Events-	10 11
	General Inquiry (SAFTEE-GI)	
	Clinician-Administered	15 min
	Dissociative States Scale	
	(CADSS)	
	Brief Psychiatric Rating	10 min
	Scale (BPRS) – Positive	
	Symptoms Subscale Only	
Biomarkers	Neuropsychological testing:	45 min
	Bushke, Stroop, Reaction	
	Time, Computerized	
	Continuous Performance Test	
	(CPT; 5 minutes),	
	Computerized A, Not B Timed	
	Reasoning Task (5 minutes),	
	Computerized Go-No Go Task	
	(5 minutes), WAIS-IV Coding	
	Subtest (3 minutes)	
	Subtest (5 illillutes)	
	@font-face {font-	
	family:"Cambria Math";	
	panose-1:2 4 5 3 5 4 6 3 2 4;	
	mso-font-charset:0; mso-	
	generic-font-family:roman;	
	1 gonono ioni ian'ily ionian,	

mso-font-pitch:variable; msofont-signature:-536870145 1107305727 0 0 415 0;}@font-face {fontfamily:Calibri; panose-1:2 15 5 2 2 2 4 3 2 4; mso-fontcharset:0; mso-generic-fontfamily:swiss; mso-fontpitch:variable; mso-fontsignature:-536859905 -1073732485 9 0 511 0;}p.MsoNormal, li.MsoNormal, div.MsoNormal {mso-style-unhide:no; msostyle-qformat:yes; mso-styleparent:""; margin:0in; msopagination:widow-orphan; font-size:12.0pt; fontfamily: "Times New Roman", serif; mso-fareastfont-family:"Times New Roman";}span.xxxappleconverted-space {mso-stylename:x x x appleconverted-space; mso-styleunhide:no;}.MsoChpDefault {mso-style-type:export-only; mso-default-props:yes; fontfamily: "Calibri", sans-serif; mso-ascii-font-family:Calibri; mso-ascii-theme-font:minorlatin; mso-fareast-fontfamily:Calibri; mso-fareasttheme-font:minor-latin; msohansi-font-family:Calibri; mso-hansi-theme-font:minorlatin; mso-bidi-fontfamily:"Times New Roman"; mso-bidi-theme-font:minorbidi;}div.WordSection1 {page:WordSection1;}

Please attach copies, unless standard instruments are used

# Off label and investigational use of drugs/devices

Choose from the following that will be applicable to your study

✓ Drug

Select the number of drugs used in this study

2

### Drug #1

Name of the drug
Ketamine
Manufacturer and other information

Multiple generic manufacturers.

Approval Status
No IND is required
Choose one of the following options
FDA conditions are met (see 'Rules')
Explain

This is a clinical study involving a marketed drug and the study meets all of the following

### conditions:

- 1. It is not intended to be reported to the FDA in support of a new indication for use or to support any other significant change in the labeling; and
- 2. It is not intended to support a significant change in the advertising for the product; and
- 3. It does not involve a route of administration or dosage level, use in a subject population, or other factor that significantly increases the risks (or decreases the acceptability of the risks) associated with the use of the product; and
- 4. It is conducted in compliance with the requirements for IRB review and informed consent [21 CFR parts 50 and 56 respectively]; and
- 5. It is conducted in compliance with the requirements concerning the promotion and sale of drugs [21 CFR 312.7].

### Drug #2

Name of the drug

[11C]UCB-J

Manufacturer and other information

[11C]UCB-J will be synthesized in the radioligand lab of the Columbia PET Center.

**Approval Status** 

IND is approved

IND#

146646

Who holds the IND/IND sponsor?

IND is held by PI/CU Investigator

[name]

# **Research Related Delay to Treatment**

Will research procedures result in a delay to treatment?

Yes

Maximum duration of delay to any treatment

Patients on an antidepressant regimen at enrollment will continue their current antidepressant regimen; there will be no delay to that ongoing treatment for those participants. The delay to inpatient admission will not exceed 3 weeks; if a participant needs a longer delay between consent and beginning treatment for logistical reasons, it will be determined by the study clinician on a case-by-case basis based on need for delay, clinical stability, and ability to comply with the plan for monitoring. This period allows the time required for processing lab samples, completion of baseline research measures, and scheduling inpatient admission, the infusion procedures in the BSU, PET, and MRI procedures.

The delay to ketamine infusion will not exceed 4 weeks from the time of enrollment.

Thus, for participants not on an antidepressant regimen at the time of enrollment, the delay to the inpatient milieu, which has a therapeutic component, will not exceed 3 weeks, and the delay to pharmacologic intervention of ketamine will not exceed 4 weeks.

Maximum duration of delay to standard care or treatment of known efficacy

For participants not already taking an antidepressant, open pharmacologic antidepressant treatment will begin as soon as post-ketamine PET scan is completed; this will not exceed 7 weeks from the time of enrollment.

Treatment to be provided at the end of the study

Pharmacologic treatment will proceed as follows at the conclusion of post-infusion PET and MRI acquisition:

Study participants will receive six months of open clinical treatment in the form of:

- a) Continuation of inpatient treatment for as long as is clinically indicated, followed by
- b) Outpatient psychiatrist visits for medication management with a psychiatrist in MIND to complete a total of 6 months of psychiatric care inclusive of the inpatient stay.

### **Clinical Treatment Alternatives**

Clinical treatment alternatives

Many treatments for MDD exist, such as numerous approved antidepressant medications, electroconvulsive therapy, and various evidence-based psychotherapies.

### Risks/Discomforts/Inconveniences

Risks that could be encountered during the study period

### 1. PET Scan-Related Risks:

#### 1A. Radiotracer

### 1A. Radiation exposure (PET)

For [C]UCB-J, the single scan injected dose limit is 740mBq or 20 mCi, yielding a cumulative protocol dose limit over two [C]UCB-J PET scans of 1480 mBq or 40 mCi. Single injection and annual exposures for all organs, as well as effective dose, are below limits set in 21CRF part 361.1. The risk estimate is based on the subjects in the study population who are most sensitive to radiation exposure.

Radiation			740MBq	
Dosimetry			dose	740MBq dose x 2
	Organ	μSv/MBq	mSv	mSv

Active Blood-forming Organs	Red marrow	0.71	0.525	1.1
Gonads	Ovaries	0.64	0.48	0.96
3 highest organs	Liver	19.9	14.73	29.5
	Brain	17.4	12.88	25.8
	Kidneys	12.6	9.32	18.6
Whole Body		5.328	3.94	7.9
Effective Dose + 2 low dose CT attenuations per PET scan		3.32	2.55	5.09
Ref: J Nucl Med 2016; 57:777– 784				

Transmission Scan NOTE: We plan to do the scans on the mCT scanner where the attenuation correction is done with a low-dose CT and therefore there will be a small amount of radiation due to the CT. In the event that the subject needs to leave the scanner while scanning (e.g. to use the bathroom) we will perform an additional low dose CT transmission scan (maximum total exposure from four CT scans ~0.176 mSv).

### 1B. Radiotracer physiological effects:

Consistent with previous work with [\$^{11}\$C]UCB-J\$ (17), we will limit injected mass to 10 micrograms. The safety of [11C]UCB-J\$ at similar injected masses has been demonstrated in PET studies published in the literature, including 10 healthy volunteers and 3 individuals with epilepsy in this study (17); five of whom received repeat [11C]UCB-J\$ injections and scans the same day (20). Another study performed PET imaging with [\$^{11}\$C]UCB-J\$ on 10 individuals with amnestic mild cognitive impairment and 11 individuals who were cognitively normal (21). The risk of an idiosyncratic reaction is acknowledged in the consent form. A physician will be **available** at the time of each injection of the radiotracer. Any adverse reaction to the radioactive drug (radiation related or not) will be reported to the NYPSI IRB and the JRSC.

### 1C. Placement of Intra-arterial catheter

Radial arterial catherization is needed for repeated arterial blood samples to construct tracer input curves. Complications resulting from such short-term catheterizations include bleeding, occlusion, clotting, or infection.

The following paragraph appears in the subject consent forms as per the IRB website, with one phrase added [shown here in italics] for more clarity for participants with lack of mathematical skills:

"The placement of a catheter in your artery may cause discomfort. There is a very small chance of complications from this catheter such as bleeding, bruising, infection or blood clot. There is an extremely low risk (0.09%, or about 1 in a thousand) of cutting off circulation to your hand which could result in a need for surgical repair or, in rare instances, could result in the loss of use of part of or all of the hand. These complications are rare and usually occur in medically ill patients who have catheters in their wrists for several days. In contrast, the catheter will remain in your arm for about four hours for this study. If you have a history of a bleeding disorder or are taking certain medications that affect blood clotting, you will not be asked to participate in this study."

The radial artery catheter is placed by an experienced physician.

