### Inclusion/Exclusion Criteria

Name the subject group/sub sample Depressed adults with current MDD

Create or insert table to describe the inclusion criteria and methods to ascertain them

Inclusion	Method of Ascertainment
1. Unipolar, major depressive episode (MDE),	1. DSM-5 criteria by SCID-5 administered by
with 17-item Hamilton Depression Rating	trained assessors; Medication history; Clinical
Scale score ≥16. Patients may be psychiatric	evaluation; Hamilton Depression Rating Scale
medication- free, or if currently taking	
psychiatric medication, not responding	
adequately as evidenced by current MDE.	
2. 18-55 years old	2. Interview
3. Female patients of child-bearing potential	3. Interview
must be willing to use an acceptable form of	
birth control during study participation such as	
condoms, diaphragm, oral contraceptive pills.	
4. Must be enrolled in IRB #4815 (PI:	4. Interview
[name])	
5. Able to provide informed consent	5. Interview. For individuals who are initially

	recruited as inpatients, an inpatient psychiatrist unaffiliated with the study will provide independent assessment of capacity.
6. Agrees to voluntary admission to an inpatient research unit at NYSPI for baseline PET/MR imaging, ketamine infusion, and repeat PET imaging	6. Interview

Create or insert table to describe the exclusion criteria and methods to ascertain them

EXCLUSION	METHOD OF ASCERTAINMENT
1. Unstable medical or neurological illness including: A) baseline hypertension (BP>140/90); B) significant history of cardiovascular illness; C) Platelet count < 80,000 cells/uL; and D) Hemoglobin < 11 g/dL for females and < 12 g/dL for males	1. Medical history, laboratory testing, all through IRB #4815
2. Significant ECG abnormality (e.g., Ventricular tachycardia, evidence of myocardial ischemia, symptomatic bradycardia, unstable tachycardia, second degree (or greater) AV block).	2. Baseline ECG
3. Pregnancy, currently lactating, or planning to conceive during the course of study participation.	3. History, baseline serum pregnancy test. Urine pregnancy tests will be repeated on the days of each MRI and PET scan, as well as one- to two-weeks after the second PET scan.
4. Diagnosis of bipolar disorder or current psychotic symptoms.	4. Clinical assessment and baseline SCID-5
5. Current or past ketamine use disorder (lifetime); any drug or alcohol use disorder within past 6 months	5. Clinical assessment, SCID, urine drug screen.

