### 1E. Blood Drawing (PET, screening)

The risks associated with drawing blood are slight discomfort and occasional bruising. The total volume drawn through enrollment in this study and co-enrollment in our area's umbrella protocol, IRB #4815, is 243ml, which is less than the volume drawn during blood donation. We exclude individuals who are anemic with a Hemoglobin value <11 g/dL for females or <12 g/dL for males.

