### 1G. Pregnancy (PET, MRI, Ketamine)

Studies involving radiation are contraindicated during pregnancy because of possible risk to the fetus. Patients must agree at the time of consent to use an effective form of birth control and to inform the treating psychiatrist in the event of pregnancy while in the study. Women of child-bearing potential will have a serum pregnancy test administered as part of initial eligibility assessments, as well as urine pregnancy tests performed on the day of the PET and MRI scans prior to scanning, and within a day prior to each ketamine infusion. On the day of the PET scan, research staff will ask female participants whether they have had sex without birth control within two weeks of the PET scan. If they have, they will not be scanned that day. An additional urine pregnancy test will be administered one to two weeks after the second PET scan. The post-PET pregnancy test can be completed at NYSPI or by a take home urine pregnancy test (test kit to be provided by the study team) with email the subject informing the research team of the

results. Subjects will not be charged for the pregnancy test. In addition, nursing mothers will also be excluded from the study.

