### 2. Side Effects of Intravenous Ketamine.

2A. Medical Risks related to Ketamine

Administration of sub-anesthetic doses of ketamine i.v., such as the 0.5 mg/kg dose to be used in this study, may induce a modest rise in blood pressure. We have administered sub-anesthetic doses of ketamine i.v. (0.5mg/kg over 40 minutes) in the setting of an IRB-approved MRI/MRS brain imaging protocol at this institution (IRB #5786, PI: [name]). The modest increases all peaked and largely resolved by 75 minutes, with vitals returning to near baseline.

In addition, ketamine may produce nausea and vomiting.

Procedures for minimizing risks related to Ketamine infusion:

Any medical risks from increased blood pressure will be minimized through the careful screening of potential subjects. Subjects will be excluded for baseline hypertension or any history of cardiovascular illness. A BLS-certified physician who has been trained in the infusion procedure will be present during the procedure. Procedures for hypertension that occurs during the infusion are described above under Study Procedures. Nausea and vomiting will be treated supportively and, if severe, with anti-emetic agents; if necessary, administration of ketamine will be discontinued. Subject will be informed that they should be fasting (12 hours no food, 4 hours no liquids) prior to the ketamine infusion.

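### The consent wording bars people with a bleeding disorder or on clotting medication, but neither the exclusion table nor the arterial line procedure carries that rule

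*Combined protocol and SAP*

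**What the plan says.** Under Risks, section 1C (Placement of Intra-arterial catheter), the protocol reproduces a paragraph of the consent form, introduced with the words "The following paragraph appears in the subject consent forms as per the IRB website". The paragraph lists bleeding among the possible complications and ends by telling the candidate that with a "history of a bleeding disorder or are taking certain medications that affect blood clotting, you will not be asked to participate". That sentence bars the person from the study, not only from the arterial line. The medications are not named there or elsewhere in the document.

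The Inclusion/Exclusion Criteria section sets out 15 numbered exclusion rows, each with a method of ascertainment. The nearest is row 1, which opens "Unstable medical or neurological illness including" and has four lettered items: hypertension, significant cardiovascular history, "C) Platelet count < 80,000 cells/uL", and low haemoglobin. Its method of ascertainment is "Medical history, laboratory testing, all through IRB #4815".

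The arterial line is described in Procedures, 5. Pre-Infusion Research Measures, item e. A physician places it after an Allen test and local anaesthetic. If the catheter cannot be placed, venous sampling may be used instead. Section 7 (Post-infusion Neuroimaging) repeats the PET procedure in identical form, so the same steps govern both scans.

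**The concern.** Two parts of one protocol give different answers to the same eligibility question. Staff normally work from the exclusion table when deciding who may enter. A candidate with a well-controlled bleeding disorder and a normal platelet count, or one taking an anticoagulant, can clear every row and go on to radial artery puncture. The form that candidate signs says such people are not invited.

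What is at stake is participant safety and the accuracy of a statement made to participants. Because the drugs are not listed, two members of staff reading the same medication list could reach different decisions. Candidates may be on continuing psychiatric medication, so staff will be reading such lists routinely.

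**Working it through.** No arithmetic applies and the plan gives no figure to reproduce. The check sets the stated rule beside each place where it would have to operate.

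1. **The rule.** Risks, 1C has two limbs: a past or present bleeding disorder, and current use of certain drugs that affect clotting. Either one bars participation.

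2. **Exclusion table, bleeding-disorder limb.** Of the 15 rows, 0 name a bleeding disorder. Row 1 is confined to unstable illness, so a stable disorder falls outside its opening words. Item 1C reaches low platelets only. It does not reach a clotting-factor defect or a platelet-function defect with a normal count. Item 1D (haemoglobin) addresses anaemia, not clotting.

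3. **Exclusion table, medication limb.** Of the 15 rows, 0 name an anticoagulant or antiplatelet drug. Two rows concern current medication: row 13 (opioids and naltrexone) and row 14 (daily benzodiazepines and named hypnotics). Item 1B (significant cardiovascular history) may remove some anticoagulant users through the underlying illness, but not all of them.

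4. **Table footnotes.** These deal with radiation exposure and scanner fit. They add nothing on bleeding.

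5. **Screening steps.** Procedures, 1. Screening provides a medical evaluation under protocol #4815, an electrocardiogram, and final eligibility once laboratory results are in. No step names bleeding history or clotting drugs.

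6. **Point of use.** Procedures, 5, item e requires the Allen test and local anaesthetic. It includes no review of bleeding history or current drugs. The venous fallback is triggered by failure to place the catheter, not by bleeding risk.

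7. **Discontinuation criteria.** Item b lets the PI withdraw anyone for whom continuing is medically unwise. That is a general discretion and does not restate the exclusion.

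The rule therefore appears in the risk text and the consent form. It is absent from the eligibility table, the screening steps and the line procedure.

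**The case against.** The strongest reply is that the protocol does state the exclusion and has several routes to enforce it. The sentence is in the consent form. Procedures, 1. Screening, item d has the consenter review that form with the candidate, and Consent Procedures, item 4 has a research MD explain the study before signature. The Risks section closes by saying that risk-minimising procedures are given within that section, so 1C can fairly be read as a safeguard in its own right. Candidates also have a medical evaluation, a Past and Current Medications List is among the instruments, and a physician places the line.

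Much of this stands. A reader might infer that no safeguard is connected to this exclusion, or that such a person would go unnoticed. The documents support neither reading. The consent discussion puts this very sentence before each candidate, and the contents of #4815 and #6879R cannot be seen here.

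Two further inferences should also be resisted:

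- **That this is the one exclusion in the risk text that never reached the table.** That depends on how loosely items are matched. The sentence in the ketamine risk section that begins "Subjects will be excluded for baseline hypertension" goes on to bar any cardiovascular history, whereas item 1B requires a significant one. That carry-over is imperfect too. Item 1C itself touches on bleeding risk.
- **That projected enrolment multiplied by two scans measures the exposure.** It counts every possible arterial line, not lines placed in people at raised bleeding risk.

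The objection does not remove the mismatch. Gathering information is not the same as having a criterion: once a bleeding disorder or anticoagulant is found, no row makes the person ineligible. A consent discussion also relies on the candidate recognising that an undefined phrase applies to them.

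**Conclusion.** The inconsistency is real and can be verified from the text: the consent wording excludes a group that the eligibility table would admit, and the line procedure has no check that would separate them. It merits a minor to should-fix rating. The safeguards already present keep it from being more serious. It stays above trivial because it concerns arterial puncture and a categorical statement to participants.

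The number of people affected is unknown, no harm rate is claimed, and the planned analysis is not affected. The conclusion assumes that the exclusion table is the operative eligibility instrument, and that #4815 and #6879R, which are not available, do not impose the same exclusion. If either of those protocols does, the table should still say so or refer to it.

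**What to change.** Add one exclusion row, for example: *Past or present bleeding disorder, or current use of a drug that impairs clotting (drugs listed by the sponsor, anticoagulants at minimum)*. Whether antiplatelet drugs belong on the list is for the sponsor to decide. Ascertain the row by medical history and the Past and Current Medications List, which is already in use.

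Add one sentence to Procedures, 5, item e: bleeding history and current medications are rechecked before each arterial line, at both scans. Anyone found to meet the exclusion does not receive an arterial line. Because the consent wording bars such people from the study and not just from the line, venous sampling should not become a way of enrolling them. Keep it for a concern that first arises after enrolment, and flag the scan in the data. Aim 1 compares V_T before and after ketamine within the same person, and a pair with one arterial and one venous input may not be comparable.

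The cost is a protocol amendment of one row and one sentence, a few candidates made ineligible, and possibly an occasional flagged scan pair.
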